**Table 2: Aims, Hypotheses, and Associated Measures**

*Pre-bereavement measures collected at baseline, 14, 30, 90, and 150 days (follow-up data collection post 150 days will occur every 6 weeks until participant transitions to bereavement). Post-death measures collected at transition, 14, 30, 90, 150 and 180 days. During study wind down, participants will complete their final data collection measure based on where they are at in the intervention (e.g., if a participant is on day 90 of 150, they will complete day 90 survey as their final measure).*

Specific Aim	Hypotheses (H) and Research Questions (RQ)	Instruments and Variables	Description
Aim 1: Determine the efficacy of the Caregiver Speaks intervention in reducing depression and anxiety among hospice family caregivers of PLWD.	RQ1: What is the effect of the Caregiver Speaks intervention on caregivers' depression, anxiety (outcomes of interest)? H1a: Family caregivers receiving the intervention will	Primary Outcome: Depression Patient Health Questionnaire (PHQ-9) Secondary Outcome: Anxiety Generalized	PHQ-9: a 9-item screening tool and severity measure for depressive mood.  Internal Consistency: .87 

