### **Data Analysis Plan:**

**Statistical Assumptions.** We will examine linearity and homoskedasticity by calculating and plotting residuals and Cook's distance for all models. Where data are missing, we will use the Last Observation Carried Forward (LOCF) missing data imputation technique, given that < 30% of data were missing for any particular subject in our prior work. If the proportion of missing data is higher, we will use regression based multiple imputation. Little's MCAR test (missing completely at random) will be used to test that missingness is in no way related to the intervention. Because the sample size is relatively large, we expect that known and unknown confounders will be distributed evenly among the two randomized groups. Additional confounders will only be introduced as covariates if we find evidence of imbalance between groups at baseline. We acknowledge that this study is not powered to detect small interaction effects.

We will test whether randomization created balanced groups by comparing baseline measures and demographic characteristics, using chi-square or t-test analysis for categorical or continuous variables, respectively. Variables that differ significantly between groups will be included in regression models as potential confounders. We will include time from study enrollment to the last observation as a covariate, as well as hospice agency. We will report estimates with 95% confidence intervals. To draw inferences from our study for the likely benefit to an equivalent population, where the intervention under trial is a model of service delivery, all analyses of outcomes will be by intention-to-treat. The intention-to-treat analysis, consistent with the objectives of a pragmatic trial, will minimize the influence of "informative missingness" of the data and preserve groups' comparability.

**Statistical Analysis.** H1a: Family caregivers receiving the intervention will report lower levels of depression and anxiety (outcomes of interest), which is facilitated by higher social support (mediating variable) than those in the control group during active caregiving.

H1b: Family caregivers receiving the intervention will report lower levels of depression and anxiety (outcomes of interest), which is facilitated by higher social support (mediating variable) than those in the control group during bereavement.

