We will examine differences between longitudinal profiles of the two study groups for each of the outcomes (PHQ-9, GAD-7, and grief intensity). We will use linear mixed effect repeated measurement (MMRM) (see model below). This will allow us to draw inferences about how our outcome measures (PHQ-9, GAD-7 and grief intensity) change over time ( $\text{slope} = \beta_{(1,T)}$  and  $\beta_{(1,C)}$ ) between the two study groups. Mixed models are able to accommodate differing numbers of measurements at varying time intervals for participants. Additionally, we will examine how social support mediates our outcomes of interest (depression, anxiety, and grief intensity). As described above, we will also include covariates where indicated.

$$\begin{aligned}
 Y_{ij} &= \beta_{-}(0,T) + \beta_{-}(1,T) t_{ij} + b_{-}oi + e_{-}ij && \text{for Treatment group} \\
 &= \beta_{-}(0,C) + \beta_{-}(1,C) t_{ij} + b_{-}oi + e_{-}ij && \text{for Control group}
 \end{aligned}$$

Where  $Y_{ij}$  represent the depression/anxiety score of the  $i^{th}$  subject at the  $j^{th}$  time,  $\beta_{-}(1,T)$  and  $\beta_{-}(1,C)$  represent the slopes for the treatment and control group respectively with intercepts that vary about the respective mean intercepts  $\beta_{-}(0,T)$  and  $\beta_{-}(0,C)$ .

H1c: Among the intervention group, family caregivers with higher baseline depression scores will experience a larger reduction in depression compared to those with less depression at baseline.

A multiple linear regression model will be used as for H1a above to examine the modifying effect of baseline PWBS score. If the  $\beta_2$  coefficient is negative and statistically significant, we will conclude that the effects of the Caregiver Speaks intervention are conditional on baseline perceptions after adjusting for duration of caregiving (time).

$$\text{Last post-baseline Anxiety/depression} = \beta_0 + \beta_2 * [\text{baseline anxiety/depression}] + \beta_3 * [\text{time}]$$

H2: Bereaved family caregivers receiving the intervention will report lower grief intensity (outcome of interest) than those in the control group.

A linear mixed effect model similar to those used for H1a and H1b will be used to examine H2, where the  $Y_{ij}$  will represent the grief intensity score for a subject of the  $i^{th}$  subject at the  $j^{th}$  time.

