# **Caregiver Speaks Data Analysis Plan**

**January 5, 2019**

**NCT04103580**

## Data Analysis

### Statistical Assumptions

We will routinely test assumptions of linearity, independence and homoskedasticity by calculating and plotting residuals and Cook's distance for all models. Where data are missing, we will substitute the mode for categorical data and the median for continuous data, given that <0.5% of data were missing for any measure in our preliminary trial. If the proportion of missing data is higher, we will use multiple imputation. In the analysis for H1a, we will use the final measure provided by caregiver before patient death, and for H1b we will use the final measure during bereavement. Because the sample size is relatively large, we expect that known and unknown confounders will be distributed evenly among the two groups. We acknowledge that this study is not powered to detect small interaction effects. Additional confounders will only be introduced as covariates if we find evidence of imbalance between groups at baseline.

We will test whether randomization created balanced groups by comparing baseline measures and demographic characteristics, using chi-square or t-test analysis for categorical or continuous variables, respectively. Variables that differ significantly between groups will be included in regression models as potential confounders. To compare outcomes for our hypotheses, we will use the last available measure post-baseline and prior to death or the end of the study and last measure during bereavement. This is a last-observation analysis.

Carpenter and Kenward argue that, in such analyses, time to this event should be taken into account. Therefore, we will include time from study enrollment to the last observation as a covariate. We will report estimates with 95% confidence intervals. To draw inferences from our study to the likely benefit to an equivalent population where the intervention under trial is a model of service delivery, all analyses of outcomes will be by intention-to-treat. The intention-to-treat analysis, consistent with the objectives of a pragmatic trial, will minimize the influence of "informative missingness" of the data and preserve groups' comparability.

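### The protocol's slope model has a random intercept but no random slope, so its slope comparison is anti-conservative if caregivers' trajectories differ

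*Protocol*

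**What the plan says.** For H1a and H1b, the protocol (section VI, Data Analysis Plan, Statistical Analysis) states: "We will use linear mixed effect repeated measurement (MMRM) (see model below"). The displayed equation gives each arm its own fixed intercept and fixed slope in continuous time, plus one random intercept per caregiver and an error term. The accompanying text describes "slopes for the treatment and control group respectively with intercepts that vary about the respective mean intercepts". The purpose is stated as: "This will allow us to draw inferences about how our outcome measures (PHQ-9, GAD-7 and grief intensity) change over time", with the two arm slopes named as the quantities of interest. H2 uses a similar model for grief intensity.

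The schedule in Table 2 is "Pre-bereavement measures collected at baseline, 14, 30, 90, and 150 days", continuing every six weeks until bereavement, and then "Post-death measures collected at transition, 14, 30, 90, 150 and 180 days".

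On model checking, the protocol says: "We will examine linearity and homoskedasticity by calculating and plotting residuals and Cook's distance for all models". The SAP says: "We will routinely test assumptions of linearity, independence and homoskedasticity", and names no remedy if independence fails.

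The SAP (Statistical Analysis) also proposes mixed models with repeated measures nested in participants, to compare change over time. The only equation it displays, however, regresses the last post-baseline measure on study group, baseline and time since enrolment. Neither document states a random slope, a residual covariance structure or a robust standard error.

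**The concern.** A model with only a random intercept lets caregivers differ in level but not in rate of change. It also implies the same correlation between any two visits, however far apart. When true slopes differ between caregivers, that variation is part of the sampling error of an arm's mean slope. The written model captures only a fraction of it, through an inflated residual variance. The slope difference is the contrast tested, so this is where the omission does harm.

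The plan gives reasons to expect varying slopes. H1c supposes that intervention caregivers with higher baseline depression improve more, which means slopes that vary and correlate with the starting level. The subgroup section expects outcomes to depend on relationship, residence, patient co-morbidity and length of exposure. The Potential Risks section leaves taking part in the Facebook discussion to each participant's choice.

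At stake are the nominal 5% level and the 95% intervals for PHQ-9 (the primary outcome), GAD-7 and grief intensity, wherever the slope model is used. A larger sample does not help, because the ratio derived below does not depend on the number of caregivers.

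**Working it through.** **Reproducing a stated figure.** There is none to reproduce. The plan gives no standard error, slope variance or residual variance for this model.

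**Inputs from the documents.** Two-sided 0.05 level (protocol, Number of Subjects). Pre-bereavement visits at days 0, 14, 30, 90 and 150 (J = 5). Post-death visits at transition and days 14, 30, 90, 150 and 180 (J = 6).

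**Assumptions.** Independent errors with variance s² = 9; complete visits; the same slope SD, s1, in both arms; months of 30 days; transition taken as day 0. The intercept variance is not needed, because with balanced visits the slope estimate uses only within-caregiver information.

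**Formulas.** Let Sxx be the sum of squared deviations of visit times from their mean.

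- True variance of an arm's mean slope: (s²/Sxx + s1²)/n
- Variance the written model reports, on average: [s² + s1²·Sxx/(J − 1)]/(n·Sxx)
- With r = s1²·Sxx/s², true/model variance = (1 + r)/(1 + r/(J − 1))
- Type I error = 2·P(Z > 1.96/√ratio)

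**Pre-bereavement schedule.** The times are 0, 0.467, 1, 3 and 5 months, with mean 1.893. Sxx = 35.218 − 5 × 1.893² = 17.29.

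Worked line for an SD of true change of 2.5 points over 150 days: s1 = 2.5/5 = 0.5 per month; r = 0.25 × 17.29/9 = 0.480; variance ratio = 1.480/1.120 = 1.32; SE ratio = 1.15; type I error = 2·P(Z > 1.705) = 8.8%.

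| SD of true change over 150 days | s1 per month | True SE / model SE | Type I error |
|---|---|---|---|
| 1.5 | 0.30 | 1.06 | 6.5% |
| 2.0 | 0.40 | 1.10 | 7.5% |
| 2.5 | 0.50 | 1.15 | 8.8% |
| 3.75 | 0.75 | 1.28 | 12.6% |
| 5.0 | 1.00 | 1.40 | 16.3% |

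In absolute terms, 234 × 0.7 gives about 164 per arm after the stated 30% attrition. At s1 = 0.5 the SE of the slope difference is √[2(9/17.29 + 0.25)/164] = 0.097 points per month. The model would report √[2(9 + 0.25 × 17.29/4)/(164 × 17.29)] = 0.084.

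**Simulation check.** The written model was fitted by REML with 164 per arm and 600 replicates. At s1 = 0.25, 0.5 and 0.75, type I error was 6.2%, 8.3% and 12.7% with complete data. With follow-up cut short by death (assumed exponential, mean 2.5 months) it was 5.8%, 8.5% and 12.2%. The closed form gives 6.0%, 8.8% and 12.6%. Monte Carlo error, √[p(1 − p)/600], is about 1 percentage point.

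**Post-death schedule** (Sxx = 31.35, J = 6). s1 = 0.25, 0.5 and 0.75 gives 7.0%, 12.0% and 17.9%.

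**Where it disappears.** With exactly two visits at the same spacing for everyone, J − 1 = 1 and the ratio is 1. With three visits over 30 days and s1 up to 0.75, the SE is understated by less than 3%, even if the residual variance is as low as 2.75 (= 5.5/2).

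**Sensitivity to the one variance the plan states.** The Number of Subjects section gives a variance of 5.5 for change in PHQ-9. A residual variance of 9 implies a two-visit change variance of at least 2 × 9 = 18, so the two do not agree. Suppose 5.5 is the whole variance of change from day 0 to day 150. The SD of true change cannot then exceed √5.5 = 2.35, and s² = (5.5 − SD²)/2:

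- SD 1.0: s² = 2.25, r = 0.04 × 17.29/2.25 = 0.307, type I error 7.5%.
- SD 1.5: s² = 1.625, r = 0.09 × 17.29/1.625 = 0.958, type I error 11.9%.

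This reading rules out the last three rows of the table (2.5, 3.75 and 5.0 points), but it does not remove the inflation.

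**The case against.** Four points on the other side carry weight.

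First, a reader might infer that the primary PHQ-9 test is known to exceed 5%. The documents do not support that. The inflation depends on slope variation that they never quantify, and it vanishes or is trivial with two equally spaced visits or very short follow-up.

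Second, independence of the errors is the usual meaning of the equation, not stated text. The MMRM label may signal an intended residual covariance, and an unstructured one would remove most of the problem. But none is specified. The label and the equation then point to different models, and the analyst cannot tell which to fit.

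Third, the slope model may not be the primary test at all. The SAP calls its comparison a last-observation analysis and displays a last-measure regression. That regression has no slope contrast, so this mechanism does not touch it. The SAP also describes mixed models of change over time, so the question is open.

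Fourth, the residual variance of 9 is not tied to this trial, and the calculation leaves out the LOCF imputation in the protocol. Both stand as limits on the figures. Neither changes the direction.

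A reader might also count the separate arm intercepts, or the absence of categorical visits, as errors. They are not. Separate intercepts cost some efficiency but do not inflate type I error. A straight line in time is a modelling choice, for which the protocol plans a linearity check.

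**Conclusion.** The concern holds conditionally. As written, the protocol's mixed model allows no between-caregiver variation in slope, and nothing in either document supplies it. If slopes vary, the standard error of the slope difference is too small on both planned schedules. On the pre-bereavement schedule type I error is about 6.5% to 16% for SDs of true change of 1.5 to 5.0 points over 150 days, given residual variance 9, independent errors, complete visits and equal slope variation in both arms.

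Confidence is high about the missing term and the direction, and low about the exact percentages. The planned checks would not reliably catch the problem: the protocol's do not address the covariance, and the SAP's check of independence leads to no stated action. The finding is confined to the mixed slope model.

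**What to change.** In the protocol's Statistical Analysis section and in the SAP's mixed model, for H1a, H1b and H2:

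1. Add a caregiver-level random slope, with a freely estimated correlation with the random intercept.
2. Use robust standard errors clustered on the patient. The Recruitment Process section assigns randomisation by patient, with all of a patient's caregivers in the same arm.
3. State the covariance assumed for the errors, and either drop the MMRM label or make the equation match it.
4. State in both documents whether the mixed slope model or the last-measure regression is primary for PHQ-9.

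The cost is a wording change and somewhat wider intervals. In the worked example the SE of the slope difference goes from about 0.084 to about 0.097 points per month, which is what the data would justify.

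A categorical-visit MMRM with unstructured covariance, or a common baseline mean, is an optional alternative. The MMRM would shift the question to a contrast at a named visit, and it sits awkwardly with the open-ended six-weekly visits before bereavement.

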	
report lower depression and anxiety (outcomes of interest), which is facilitated by higher social support (mediating variable) than those in the control group during active caregiving.
 
H1b: Family caregivers receiving the intervention will report lower depression and anxiety (outcomes of interest), which is facilitated by higher social support (mediating variable) than those in the control group during bereavement.
 
H1c: the intervention group, family caregivers with higher baseline depression scores will experience a larger reduction in depression compared to those with less depression at baseline.
	
Anxiety Disorder (GAD-7)
 
Mediating Variables: Social Validation & Growth: Social Meaning in Life Events Scale –Social Validation SMILES-SV
 
Integration of Stressful Life Experiences Scale Short Form (ISLES-SF)
 
Caregiver Quality of Life Index (CQLI-R)
	
GAD-7: a 7-item screening tool and severity measure for generalized anxiety. Internal Consistency: .89
 
SMILES-SV: a 9-item tool for measuring social validation and meaning-making during stressful life events. Internal Reliability: .84
 
ISLES-SF: a 6-item measure that assess meanings made of stress during bereavement.
 
CQLI-R: a 4-item scale that measures physical, social, emotional, and financial quality of life among active caregivers.

Aim 2: Examine the effect of the Caregiver Speaks intervention on grief intensity among bereaved hospice family caregivers of PLWD
	
H2: Bereaved family caregivers receiving the intervention will report lower grief intensity (outcome of interest) than those in the control group.
	
Secondary Outcome: Grief Intensity Texas Revised Inventory of Grief (TRIG)-Present Scale
	
TRIG-Present: a 13-item scale measuring present grief among bereaved individuals. Internal Consistency: .86

Aim 3: Describe how caregivers make meaning of their caregiving and bereavement experiences
	
RQ2: In what ways do active caregivers find meaning as reflected in their FB posts?
	
Caregiver Photos, Discussion of Photos via Facebook Group, Post-intervention
	
Qualitative data triangulation and mixed methods analysis.

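### The H1c analysis does not match H1c: the named modifier is undefined and unlisted, the equation admits anxiety, and the decision rule does not test for a larger reduction

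*Protocol*

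**What the plan says.** The hypothesis (Protocol, Section VI, Data Analysis Plan, Statistical Analysis) is that, among those assigned to Caregiver Speaks, "family caregivers with higher baseline depression scores will experience a larger reduction in depression compared to those with less depression at baseline". Section I and Table 2 state it in nearly the same words. All three versions name depression only.

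The analysis follows in three pieces:

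- **Introductory sentence:** "A multiple linear regression model will be used as for H1a above to examine the modifying effect of baseline PWBS score".
- **Decision rule**, applied to β2 with time as the adjustment variable: "coefficient is negative and statistically significant, we will conclude that the effects of the Caregiver Speaks intervention are conditional on baseline perceptions".
- **Equation:** the outcome is "Last post-baseline Anxiety/depression", regressed on baseline anxiety/depression (β2) and time (β3). There is no study-group term; the numbering goes from β0 straight to β2.

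Table 2 lists six scales: PHQ-9 (depression, primary), GAD-7 (anxiety, secondary), SMILES-SV, ISLES-SF, CQLI-R and TRIG-Present. The SAP's Statistical Analysis section covers H1a, H1b and H2 and does not mention H1c.

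**The concern.** H1c is a stated hypothesis under Aim 1, and this short block is its only specification. Within it the modifier is called a PWBS score, then perceptions at baseline, then anxiety/depression, and the outcome is written for two scales although the hypothesis concerns one. Nothing says which wording governs, so the analyst must choose the instrument.

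There is also a question of whether the test, once the instrument is settled, answers H1c at all. The hypothesis is about a reduction, the outcome is a level, and the conclusion is about the effect of the intervention although only treated caregivers enter the model. If the rule is applied as written, a true H1c would be reported as unsupported. If the rule is loosened without a control group, ordinary regression to the mean could be reported as effect modification.

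**Working it through.** **1. The texts side by side**

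| Element | H1c | Introductory sentence | Decision rule | Equation |
|---|---|---|---|---|
| Modifier | Baseline depression | PWBS score | Perceptions at baseline | Baseline anxiety/depression |
| Outcome | Reduction in depression | Not stated | Effects of the intervention | Last anxiety/depression score |
| Arms | Intervention only | As for H1a (both arms) | Not stated | No group term |

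PWBS occurs once across the two documents. The reference back to H1a is also unclear: the Protocol analyses H1a with a linear mixed model, not a multiple linear regression. The SAP does display a last-measure regression for H1a, with study group as β1, and the H1c equation resembles it with that term left out.

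**2. What H1c implies for β2**

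Take the PHQ-9 form: E(last) = β0 + β2·baseline + β3·time. Subtracting baseline from both sides gives

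E(last − baseline) = β0 + (β2 − 1)·baseline + β3·time.

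A larger reduction at higher baseline means β2 − 1 < 0, so β2 < 1. The plan requires β2 < 0, which is a change slope below −1. For example, with β2 = 0.6 and two caregivers 10 points apart at baseline, the expected difference in change is (0.6 − 1) × 10 = −4 points. H1c holds, but the rule is not met.

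**3. How often the rule would be met**

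Inputs from Section V: 234 in the intervention group and 30% attrition, so 234 × 0.70 = 163.8, taken as 163. Assumptions not in the documents: baseline SD 5, residual SD 4, normal scores with no floor, follow-up time uniform over 14 to 300 days, two-sided 0.05. There were 4,000 runs per row.

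| True β2 | Change slope | H1c true? | Rule met |
|---|---|---|---|
| 1.0 | 0 | No | 0% |
| 0.8 | −0.2 | Yes | 0% |
| 0.6 | −0.4 | Yes | 0% |
| 0.4 | −0.6 | Yes | 0% |
| 0.2 | −0.8 | Yes | 0% |
| 0 | −1.0 | Yes | 2.8% |
| −0.2 | −1.2 | Yes | 88% |

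The pattern does not depend on the assumed SDs. For any true β2 of zero or more, a negative coefficient significant at two-sided 0.05 has a probability of at most about 2.5%.

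**4. Why β2 < 1 in one arm is not the remedy**

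Measurement error in the baseline score pulls the fitted slope below 1 even when there is no true modification. With true slope 1 and the same set-up, a test of β2 < 1 rejected in:

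| Assumed baseline reliability | Rejected |
|---|---|
| 0.87 | 47% |
| 0.80 | 81% |
| 0.70 | 98% |

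Table 2 gives .87 as the PHQ-9's internal consistency. That is used here only as one point in a range, since it is not reliability over time.

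**5. What would support the stated conclusion**

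Fit both arms:

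last PHQ-9 = γ0 + γ1·group + γ2·baseline PHQ-9 + γ3·(group × baseline PHQ-9) + γ4·time.

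The intervention effect at baseline score x is γ1 + γ3·x. Regression to the mean is expected equally in both randomized arms and falls into γ2. A benefit that grows with baseline depression is γ3 < 0.

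Approximate precision with 163 per arm: SE(γ3) ≈ √2 × (residual SD / baseline SD) / √163. At the assumed ratio 4/5 this is 1.414 × 0.8 / 12.77 = 0.089, so the γ3 detectable with 80% power is about (1.96 + 0.84) × 0.089 = 0.25 in size. For ratios of 0.6 and 1.0 it is about 0.19 and 0.31.

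**The case against.** The strongest reply is that PWBS is a stray label. The displayed equation has no PWBS term, and everything it needs is a Table 2 measure or a date. The slash is most naturally shorthand for one model per outcome: the Protocol writes depression/anxiety in the same way for the H1a model just above, which it fits to each outcome. The depression version then contains H1c's own variables. The mention of perceptions is loose prose and names no instrument. H1c is also separate from the between-arm comparisons in H1a, H1b and H2, which this wording does not touch.

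Most of that stands, and it rules out several stronger readings that a reader might infer:

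- *That the analysis cannot be run.* The equation can be fitted as displayed.
- *That PWBS is never collected.* No survey form is in the documents, and Table 2 is not shown to be a full inventory; the plan also uses demographic characteristics that Table 2 does not list. What can be said is that PWBS is undefined and unlisted.
- *That H1c can be declared on either scale, which inflates the false-positive rate.* Every statement of H1c names depression only, so a GAD-7 coefficient could not support it as stated. The rule also counts only negative coefficients, and it is centred on β2 = 0 although no differential reduction means β2 = 1, where the rule was met in 0% of runs.

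The reply does not remove the need to name the instrument in the sentence that defines the modifier. It also leaves the decision rule and the missing control group unanswered.

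**Conclusion.** The point holds as a mismatch between H1c and its only written analysis. The modifier is undefined and unlisted, anxiety is admitted without a label, and the SAP is silent. These are wording defects that rest on the text alone.

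The more consequential defect is the test. With a last score as outcome, β2 < 0 is the wrong criterion for a larger reduction. That follows from algebra; the simulated 0% for slopes of 0.2 to 0.8 illustrates it under the stated assumptions. A model of one arm cannot show that the intervention's effects depend on baseline, nor separate that from regression to the mean. The 47% to 98% figures depend on the assumed reliabilities and SDs.

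This should be corrected before analysis. It does not affect the main between-arm comparisons.

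**What to change.** In the Protocol's H1c text:

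1. Name baseline PHQ-9 as the modifier and PHQ-9 as the outcome. Remove PWBS, and replace the reference to perceptions at baseline with baseline depression.
2. Label any GAD-7 version exploratory.
3. Replace the single-arm equation with last PHQ-9 on study group, baseline PHQ-9, group-by-baseline PHQ-9 and time, using both arms. Base H1c on the interaction coefficient, reported with its 95% confidence interval, and drop the rule that β2 be negative.
4. Reword H1c so that it compares arms, since it is now stated within the intervention group while its conclusion concerns the effects of the intervention. A within-arm description can stay if it carries no claim about those effects.
5. Put the same text in the SAP. Its displayed regression already has group, baseline and time, so one interaction term is added.

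The cost is a wording change in two documents. The PHQ-9 is a listed measure and measures are collected at baseline in both arms, so no new data are needed. The drawback is limited power for a small interaction, which the Statistical Assumptions text in both documents already concedes.

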### **V. Number of Subjects**

1. The anticipated enrollment number is 468 subjects (or 234 for intervention group and 234 for control).
2. The PHQ-9 is widely used, has good internal consistency, is well validated, and is commonly used to inquire about the degree to which an individual has experienced depressed mood over the past two weeks. Our power calculations based on our preliminary work hold the following assumptions: 1) attrition rate of 30% 2) 80% power

3) a two-sided alternative for group differences at the 0.05 level of significance for a change in PHQ-9 scores (average of 4 points, variance of 5.5).

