**Subgroup Analysis.** We will analyze several subgroups to identify unique attributes that might influence outcomes. Our subgroups are 1) hospice agency, to reflect different organizational structures, 2) older age, gender, race & ethnicity, which might influence use or understanding of Facebook, 3) Caregiver relationship to and residence with the patient, which could affect the meaning and amount of burden and 4) Time from enrollment to last observation, which reflects intervention dose, and 5), co-morbidities in patients, which may impact caregiving outcomes.

**Qualitative Analysis.** See Table 3 (below) for a detailed qualitative analysis plan. We will enter all photos, qualitative Facebook data, and transcribed interviews into qualitative coding software (Dedoose) for triangulation (use of multiple data sources to ensure a rich and robust dataset) and thematic analysis.

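### Time from enrolment to last observation is listed as a dose subgroup, but it is fixed after randomisation and can produce a false dose-response

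*Protocol*

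**What the plan says.** The Subgroup Analysis paragraph of the protocol's Data Analysis Plan opens with "We will analyze several subgroups to identify unique attributes that might influence outcomes". Item 4 on its list is "Time from enrollment to last observation, which reflects intervention dose". The other items are hospice agency, caregiver demographics, relationship to and residence with the patient, and patient co-morbidities.

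For item 4 the paragraph gives no cut-point and no treatment of the control arm, and it does not note that the variable arises after randomisation. It names no method for any of the subgroups. The nearest statement, under Statistical Assumptions, is "We acknowledge that this study is not powered to detect small interaction effects". The SAP has no subgroup section.

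The same variable also appears as a model covariate in both documents: "We will include time from study enrollment to the last observation as a covariate, as well as hospice agency" (protocol) and "Therefore, we will include time from study enrollment to the last observation as a covariate" (SAP). Both documents promise intention-to-treat for all outcome analyses.

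**The concern.** A subgroup compares like with like only if membership is settled before randomisation or cannot be affected by it. Follow-up time does not clearly meet that condition.

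- **What sets it.** The note to Table 2 makes follow-up depend on when the patient dies and on study wind-down. Section V adds dropout.
- **Why it is not dose.** Controls receive usual care only, so their days in the study measure no exposure. In the intervention arm, Section VII says participants may read and respond, or not, as they choose. Days enrolled are therefore not posts or log-ins.
- **Why arm could affect it.** Only the intervention arm has to use Facebook, which Section VII lists as a possible source of anxiety or frustration. Only that arm gets the one-week support call that Section VI introduces to help retention. Both how many leave and who leaves could differ by arm.

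If so, the long-stay caregivers in the two arms are differently selected groups. The trial could then report that longer exposure works when the pattern only reflects who stayed.

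**Working it through.** The plan states no figure for this subgroup, so there is none to reproduce. The check asks how large a false difference could be when the intervention does nothing.

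**Inputs from the protocol (Section V).** Arm size: "The anticipated enrollment number is 468 subjects (or 234 for intervention group and 234 for control"). Attrition and power: "attrition rate of 30% 2) 80% power", with attrition not split by arm. Test: "two-sided alternative for group differences at the 0.05 level of significance". The stated variance is 5.5. The table uses SD 5.5; the literal reading is SD = √5.5 = 2.35.

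**Assumptions not in the documents.** Dropout is 30/30 or 35/25 (intervention/control). The log odds of dropping out rise by b = 0.3, 0.5 or 1.0 per SD of worse score. Long follow-up is simplified to being retained, so death and wind-down are left out.

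**Formula.** With logistic dropout at average rate p and slope b, the covariance of score (in SDs) with dropout is about b·p(1-p). Dividing by the retained fraction (1-p), the retained mean falls by about SD·b·p. So

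false difference ≈ -SD × (b_T·p_T - b_C·p_C).

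A negative value looks like benefit. The approximation is good for small b and too large at b = 1.0, where the simulated values should be used.

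| Dropout (T/C) | Severity relation | Formula at b = 0.3 | Simulated, b = 0.3 / 0.5 / 1.0 | Rejection at 0.05 |
|---|---|---|---|---|
| 30/30 | same in both arms | 0 | 0 / 0 / 0 | about 5% |
| 35/25 | same in both arms | -5.5×0.3×(0.35-0.25) = -0.17 | -0.16 / -0.26 / -0.43 | 6 / 7 / 12% |
| 30/30 | intervention arm only | -5.5×0.3×0.30 = -0.50 | -0.5 / -0.8 / -1.4 | 12-13 / 25-26 / 65-67% |
| 35/25 | intervention arm only | -5.5×0.3×0.35 = -0.58 | -0.6 / -0.9 / -1.6 | 15-17 / 32-34 / 77-79% |

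Ranges show the spread over repeat runs of several thousand null trials each.

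**Hand check of one rejection rate (last row, b = 0.3).** Retained: 234×0.65 = 152 and 234×0.75 = 175.5. SE = 5.5×√(1/152 + 1/175.5) = 0.61. Then 0.58/0.61 = 0.95, and Φ(-1.96+0.95) + Φ(-1.96-0.95) = 0.156 + 0.002, about 16%.

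**Literal variance.** Point differences divide by 5.5/2.35 = 2.35. The last row becomes about -0.26, -0.38 and -0.68. Rejection rates do not change.

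**A version with time to death included.** Here follow-up was 180 days plus an exponential time to death (mean 100 days, assumed), cut short by 30/30 dropout. SD was 2.35, and the outcome correlated 0.8 with the severity driving dropout. The sample was split at median follow-up; wind-down was not modelled.

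- Dropout random, or equally related to severity in both arms: no bias.
- Odds ratio 2 per SD in the intervention arm, 1 in control: -0.24 (long half) and +0.24 (short half). Each half rejected 12-13% of the time and the interaction 20.5%.
- Odds ratio 2 against 1/2, a deliberately unfavourable case: -0.47 and +0.47. Each half rejected 33-35% and the interaction 59%.
- The same unfavourable case split on a baseline variable: about 0, with 4.9-5.5% rejection throughout.

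The false pattern is benefit in long stayers and harm in short stayers, which looks like dose-response. An interaction test does not protect against it when the stratifier is follow-up time.

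**The case against.** The strongest reply is that bias needs two things together: follow-up related to outcome, and affected by arm. A caregiver intervention is unlikely to change when the patient dies or when the study winds down, and these probably dilute the bias. At 30/30 dropout with the same severity relation in both arms there is none. The 35/25 split and the slopes are assumptions; the only attrition figure in the documents is 30% overall. All of this stands, and it is why the size has to be given as a range that includes zero.

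It can also be said that the plan never states that arms will be compared within follow-up strata. That is true. But item 4 sits in a list of subgroups for outcome analyses, and nothing excludes that comparison. An analysis within the intervention arm alone would still read persistence as dose.

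Three stronger inferences are tempting and not supported:

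- **That the main result is compromised.** None of H1a to H2 and no power statement rests on item 4. Its use as a model covariate is a separate question.
- **That subgroups will be tested one at a time without interaction tests.** The plan is silent on method, and its remark about interaction effects suggests they were considered.
- **That a familywise error rate can be computed for the subgroup list.** The plan gives neither levels nor number of tests. Tests on the same participants are correlated, so a calculation assuming independence would be wrong.

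**Conclusion.** The point holds in a limited form. Item 4 is a post-randomisation variable labelled as dose. That label is wrong for controls and unsupported for the intervention arm, whether or not any bias arises.

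Arm comparisons within it can mislead if dropout differs by arm in rate or in kind and is related to outcome. That is plausible here but not shown by the documents. At SD 5.5 the false difference ranges from none, through -0.2 to -0.4 points when only the rates differ, to -0.6 to -1.6 points when severity drives dropout in the intervention arm alone and the rates also differ. These figures come from a completer comparison under assumed dropout and shrink 2.35-fold if the variance of 5.5 is literal. The harm is to a secondary reading of the trial, so this should be corrected but does not threaten the primary test.

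**What to change.** 1. Delete item 4 from the subgroup list and limit subgroups to variables measured at baseline.
2. If dose is of interest, describe recorded engagement in the intervention arm (posts, log-ins) without comparing arms. Use a complier-average estimate only with a compliance definition stated in advance and the exclusion restriction acknowledged. The documents define no compliance, since participation on the page is voluntary.
3. For the baseline subgroups, name the method, which the plan does not now do. The treatment-by-subgroup interaction with its 95% interval is preferred.
4. Put the same text in the SAP, which has no subgroup section.

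Cost: wording in two documents and the loss of one exploratory table. No new arm-comparison data are needed.
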